7.2.4 Minnesota Nicotine Withdrawal Scale (revised edition) Questionnaire

The MNWS (**Hughes and Hatsukami 2008**) is a 24 hour recall that will be completed by the subject him/herself daily on Day -1 to Day 6 prior to product use to reflect the previous days experience. Therefore although it is collected on Days -1 to 6 it will be reported as Days -2 to 5.

The self-reported part of the MNWS, that was administered in this study consists of the following 15 items which are rated on a scale of 0 to 4 (see **Table 5**). Higher scores indicate greater intensity on that scale.

The total scores will be derived by calculating the average of all the non-missing data per Total Score as shown in **Table 5**. The first total score consists of the first 9 items, the second total score is based on 6 extra items which are thought to have an impact on withdrawal but have not been validated. If more than 50% of the items are missing then the total score will be set to missing.

**Table 5: Minnesota Nicotine Withdrawal Scale (Revised Edition) Questionnaire Scores**

	Question	Total Score
1	Angry, irritable, frustrated.	1 and 2
2	Anxious, nervous.	1 and 2
3	Depressed mood, sad.	1 and 2
4	Desire or craving to smoke.	1 and 2
5	Difficulty concentrating.	1 and 2
6	Increased appetite, hungry, weight gain.	1 and 2
7	Insomnia, sleep problems, awakening at night.	1 and 2
8	Restless.	1 and 2
9	Impatient.	1 and 2
10	Constipation	2
11	Dizziness	2
12	Coughing	2
13	Dreaming or nightmares	2
14	Nausea	2
15	Sore throat	2

7.2.5 Human Puffing Topography Questionnaire

A specific subject self-reported questionnaire, used for exploratory purposes, has been developed by PMI to evaluate the impact of the use of the HPT SODIM[®] device on smoker's puffing experience in terms of ritual disruption. This is a questionnaire with 5 items to be rated on a 5-point scale (strongly agree, agree, neither agree nor disagree, disagree and strongly disagree) and an open question for each item in case the subject agrees or strongly agrees (**Table 6**). Subjects will be asked by the Investigator or designee to complete the HPT questionnaire at:

On Day -2, HPT and HPT questionnaire will be done in all subjects using CC compatible with the HPT SODIM[®]

On Day 1 and Day 4 in the confinement period, HPT and HPT questionnaire will be done in all subjects in the CHTP and CC arms. Puffing topography with the HPT SODIM[®] device will not be done in subjects using CC that are incompatible with the HPT SODIM[®] device (e.g., slim CC).

Table 6: Human Puffing Topography Questionnaire

Question
Smoking of the conventional cigarettes or using of the tested products is different with the device.

**Table 6: Human Puffing Topography Questionnaire**

Question
You enjoy smoking the conventional cigarettes or using of the tested products with the device as much as without it.
The taste of the conventional cigarette or of the tested products is different with the device.
The device is easy to use.
Your smoking of the conventional cigarettes or your using of the tested products is disturbed by the device.

7.2.6 Cough Assessment

Subjects will be asked to assess the respiratory symptom ‘cough’ using a VAS, three Likert scale questions, and one open ended question on a daily basis during the confinement period (on Day -1 to Day 6) prior to 11:30 AM or at 06:29 AM \pm 1 hour on Day 6.

Subjects will be asked if they have experienced a regular need to cough, e.g., whether they have coughed several times in the previous 24 hours prior to assessment. If the answer is ‘yes’, subjects will be asked to complete questionnaire.

The VAS will assess how bothersome cough is to the subject ranging from ‘not bothering me at all’ to ‘extremely bothersome’, and this will be given a numeric value between 0 and 100, measured on a 100 mm scale.

Subjects will also be asked to assess the intensity and frequency of cough and the amount of sputum production on Likert scales as presented in **Table 7**.

Table 7 Cough Assessment Likert Scales

Question	Likert Scale
1 The intensity of cough	1 = very mild 2 = mild 3 = moderate 4 = severe 5 = very severe
2 The frequency of cough	1 = rarely 2 = sometimes 3 = fairly often 4 = often 5 = almost always
3 The amount of sputum production	0 = no sputum

**Table 7 Cough Assessment Likert Scales**

Question	Likert Scale
	1 = a moderate amount of sputum;
	2 = a larger amount of sputum;
	3 = a very large amount of sputum.

Open question: Are there any other important observations that you would like to share with us about your coughing?

7.3 Human Puffing Topography Assessment

The HPT SODIM[®] device measures and records the flow and other per-puff parameters listed below (Table 8). From the per-puff parameters, the per-cigarette parameters shown below will be derived (representing average values or totals per cigarette (Table 9)). Prior to calculation of the per-cigarette parameters, the topography data will be processed through analysis software. Only data that are able to be processed by the software will contribute to the per-cigarette parameters and will be part of the study database.

Table 8:HPT- Per-Puff Parameters

Description	Variable	Unit
Puff number	N _i	
Puff volume	V _i	mL
Puff duration	D _i	S
Average flow [V _i /D _i]	Q _{mi}	mL/s
Peak flow	Q _{ci}	mL/s
Inter puff interval	I _i	S
Sum of I _i and D _i	D _{fi}	S
Work [INT P _{mi} *FinalFlow*dt]	W _i	mJ
Average pressure drop	P _{mi}	mmWG
Peak pressure drop	P _{ci}	mmWG
Average resistance [P _{mi} /Q _{mi}]	R _{mi}	mmWG/mL/s
Peak resistance [P _{ci} /Q _{ci}]	R _{ci}	mmWG/mL/s
Number of peak(s) in the puff	P _n	

Table 9:HPT - Per-CHTP / Cigarette Parameters

Description	Variable	Formula	Unit
Total number of puffs	NPC	$\sum N_i$	
Total puff volume	TVOL	$\sum V_i$	mL
Average puff volume	AvgV _i	$\sum V_i / NPC, i=1 \dots NPC$	mL

Table 9: HPT - Per-CHTP / Cigarette Parameters

Description	Variable	Formula	Unit
Average puff duration	AvgDi	$\Sigma Di / NPC, i=1 \dots NPC$	s
Total puff duration	TDi	ΣDi	s
Average flow	AvgQmi	$\Sigma Qmi / NPC, i=1 \dots NPC$	mL/s
Peak flow	AvgQci	$\Sigma Qci / NPC, i=1 \dots NPC$	mL/s
Total inter puff interval	Tli	ΣIi	s
Average inter puff interval	AvgIi	$\Sigma Qci / NPC, i=1 \dots NPC$	s
Total smoking duration	TDFi	ΣDFi	s
Total work	TWi	ΣWi	mJ
Average work	AvgWi	$\Sigma Wi / NPC, i=1 \dots NPC$	mJ
Average pressure drop	AvgPmi	$\Sigma Pmi / NPC, i=1 \dots NPC$	mmWg
Average peak pressure drop	AvgPci	$\Sigma Pci / NPC, i=1 \dots NPC$	mmWg
Puffing intensity	SMINT	TVOL/TDFi	mL/s
Puffing time index	PTI	$(100*TDi)/TDFi$	%
Puff frequency	PFeq	$NPC/(TDFi/60)$	Min ⁻¹
Average puff volume per peak	AvgVpn	$\Sigma (Vi/Pn) / NPC, i=1 \dots NPC$	mL/s
Average puff duration per peak	AvgDpn	$\Sigma (Di/Pn) / NPC, i=1 \dots NPC$	s

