7.7.2 Human Puffing Topography Parameters

The HPT SODIM® device measures and records the flow and other per-puff parameters listed in Table 4 below. From the per-puff parameters (Table 4), the per-cigarette parameters shown in Table 5 will be derived (representing average values or totals per cigarette).

Prior to calculation of the per-CHTP 1.0/CC parameters, the Sponsor's HPT group will validate the data and discard any invalid data. Only valid data for the per-CHTP/cigarette parameters will be part of the study database and will be analyzed.

Table 4 Human Puffing Topography – Per-Puff Parameters

Description	Variable	Unit
Puff number	Ni	
Puff volume	Vi	ml
Puff duration	Di	s
Average flow [Vi/Di]	Qmi	ml/s
Peak flow	Qci	ml/s
Inter puff interval	li	s
Sum of li and Di	DFi	s
Work [INT Pmi*FinalFlow*dt]	Wi	mJ
Average pressure drop	Pmi	mmWG
Peak pressure drop	Pci	mmWG
Average resistance [Pmi/Qmi]	Rmi	mmWG/ml/s
Peak resistance [Pci/Qci]	Rci	mmWG/ml/s

Table 5 Human Puffing Topography – Per-CHTP 1.0/Cigarette Parameters

Description	Variable	Formula	Unit
Total number of puffs	NPC	$\sum Ni$	
Total puff volume	TVOL	$\sum Vi$	ml
Average puff volume	AvgVi	$\sum Vi / NPC, i=1 \dots NPC$	ml
Average puff duration	AvgDi	$\sum Di / NPC, i=1 \dots NPC$	s
Total puff duration	TDi	$\sum Di$	s
Average flow	AvgQmi	$\sum Qmi / NPC, i=1 \dots NPC$	ml/s
Peak flow	AvgQci	$\sum Qci / NPC, i=1 \dots NPC$	ml/s

Confidentiality Statement

Data and information contained in this document are considered to constitute trade secrets and confidential commercial information, and the legal protections provided to such trade secrets and confidential information are hereby claimed under the provisions of applicable law. No part of this document may be publicly disclosed without the written consent of Philip Morris Products S.A.

Description	Variable	Formula	Unit
Total inter puff interval	Tli	$\sum li$	s
Average inter puff interval	Avgli	$\sum Qci / NPC, i=1 \dots NPC$	s
Total smoking duration	TDFi	$\sum DFi$	s
Total work	TWi	$\sum Wi$	mJ
Average work	AvgWi	$\sum Wi / NPC, i=1 \dots NPC$	mJ
Average pressure drop	AvgPmi	$\sum Pmi / NPC, i=1 \dots NPC$	mmWg
Average peak pressure drop	AvgPci	$\sum Pci / NPC, i=1 \dots NPC$	mmWg
Puffing intensity	SMINT	TVOL/TDFi	ml/s
Puffing time index	PTI	$(100*TDi)/TDFi$	%
Puff frequency	PFeq	$NPC/(TDFi/60)$	Min ⁻¹

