12.5.3.2 Human Puffing Topography Parameters

The HPT assessments will take place on Day -2, Day 1 and Day 4 in the CHTP and CC arms, if CC are compatible with the HPT SODIM[®] device.

The per puff parameters are shown in Table 8 and the per cigarette parameters are shown in Table 9.

The per-cigarette parameters derived from the HPT assessments will be summarized along with their changes from baseline. The per-puff and per-cigarette parameters will be listed. In addition the geometric mean and 95% CI of the geometric mean of the per-cigarette parameters will be presented graphically.

The per-cigarette parameters will be analyzed on Days 1 and 4 separately using an ANCOVA model on the log-transformed HPT parameter with terms for log-transformed baseline score, sex, average daily CC consumption over the last 6 weeks as reported during screening, product.

The SAS code will be the same as described in Section 12.5.1.1 “COHb in blood and urinary concentrations adjusted for creatinine of MHBMA, 3-HPMA and S-PMA in 24 hour collection”.

LS means for each product along with the reduction (i.e. 100% - ratio of CHTP : CC) and 95% CI will be presented in the tables.

All figures, summaries and analyses will be performed on the FAS.

The data will be presented in the below outputs, the TFL number refers to the TFL number in the accompanying TFL shell document:

TFL number	Title
TABLES	
15.2.4.30	Descriptive Statistics of HPT Parameters per Cigarette – FAS
15.2.4.31	Analysis of HPT per Cigarette – FAS
FIGURES	
15.1.2.37	HPT per Cigarette Parameters Geometric Mean and 95% CI – FAS
LISTINGS	
15.3.7.1	Listing of HPT Assessments

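### The printed formula for total puffs per stick, a sum of puff numbers, would not return a puff count if programmed as written; the SAP should define it as the count of valid puffs

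*SAP*

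**What the plan says.** SAP Section 7.3 lists the per-puff parameters in Table 8. The first is Ni, labelled as the puff number, with no unit and no further definition. Table 9 derives the per-stick parameters, described as "representing average values or totals per cigarette". Its first row is "Total number of puffs", NPC, with the formula ΣNi and no summation limits. The average parameters divide a sum over puffs by NPC and give the limits i = 1 to NPC. Puff frequency is NPC/(TDFi/60).

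Protocol Section 7.7.2 has the same construction: "From the per-puff parameters (Table 4), the per-cigarette parameters shown in Table 5 will be derived". Neither document says whether Ni is the position of the puff in the sequence or a value of 1 for each puff.

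SAP Section 12.5.3.2 gives the use: "The per-cigarette parameters will be analyzed on Days 1 and 4 separately using an ANCOVA model on the log-transformed HPT parameter". Results are reported as 100% minus the CHTP:CC ratio.

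**The concern.** The sum of the numbers 1 to n is not n. If Ni is the ordinal, the printed rule and the rest of its own table agree only when a stick has a single puff.

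NPC is itself an analysed parameter, and other rows depend on it. In SAP Table 9, ten averages divide by it: puff volume, puff duration, flow, peak flow, inter-puff interval, work, pressure drop, peak pressure drop, and the two per-peak parameters that the SAP added. Puff frequency multiplies by it. With NPC itself, 12 of the 19 rows depend on this cell. In Protocol Table 5, eight averages divide by it.

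The error factor would depend on n. The two arms use different products, so equal puff counts cannot be taken for granted, and a literal derivation could produce an apparent difference in puffing where there is none.

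**Working it through.** **Inputs.** From the documents: NPC = ΣNi, averages = Σx/NPC over i = 1 to NPC, and puff frequency = NPC/(TDFi/60). The documents give no puff counts, so n is assumed, over a range of 8 to 20. They state no numerical result for this derivation, so there is no planned figure to reproduce.

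**Step 1: two readings of Ni.**
- Ordinal (1, 2, …, n): NPC = n(n+1)/2.
- Indicator (1 for each puff): NPC = n.

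**Step 2: effect under the ordinal reading.** NPC and puff frequency are multiplied by [n(n+1)/2]/n = (n+1)/2. Each average is multiplied by the inverse, 2/(n+1).

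| Assumed n | Printed NPC | Factor on NPC and puff frequency | Factor on averages |
|---|---|---|---|
| 8 | 36 | 4.5 | 0.222 |
| 10 | 55 | 5.5 | 0.182 |
| 12 | 78 | 6.5 | 0.154 |
| 15 | 120 | 8.0 | 0.125 |
| 16 | 136 | 8.5 | 0.118 |
| 20 | 210 | 10.5 | 0.095 |

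For example, with 12 puffs of an assumed 55 mL each, the total volume is 660 mL. The average should be 660/12 = 55 mL; the literal formula gives 660/78 = 8.46 mL.

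**Step 3: consistency with the table's own limits.** With 12 puffs, limits of 1 to NPC would call for 78 terms, and 78 − 12 = 66 of those puffs do not exist. With NPC = n the limits and the averages agree.

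**Step 4: effect on the CHTP:CC ratio.** Assume CC 12 puffs, CHTP 16 puffs, and equal true averages.
- Averages: (2/17)/(2/13) = 13/17 = 0.76 instead of 1, an apparent reduction of 24%.
- NPC: 136/78 = 1.74 instead of 16/12 = 1.33.
- Puff frequency, if truly equal: (17/2)/(13/2) = 17/13 = 1.31 instead of 1.

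With 14 CHTP puffs against 10 CC puffs, the ratio of averages is 11/15 = 0.73. With equal counts it is 1, so the distortion comes only from the difference in n.

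**Step 5: does baseline adjustment remove it?** No. The Day −2 baseline is measured on CC in every subject (Protocol Section 7.7.1), so the baseline offset is similar in both arms. The extra shift in the CHTP arm comes from that product's own puff count on Days 1 and 4.

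**Rows not affected.** Total puff volume, total puff duration, total inter-puff interval, total smoking duration, total work, puffing intensity and puffing time index do not use NPC.

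**The case against.** The strongest reply is that this is loose notation. Ni is never defined as an ordinal. With Ni = 1 for each puff the sum is n and every limit is consistent. The row label and the limits both tell a programmer that a count is meant, and the ordinal version cannot be executed as printed because the sums would run past the last puff. The SAP adds that, before derivation, "the topography data will be processed through analysis software"; the algorithm is not given. A literal result would also be conspicuous: 12 puffs would be reported as 78.

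Much of this stands. The intended meaning is clearly the count, and a reader might infer from the formula that the topography results will be corrupted. The documents do not support that inference, because nothing in them shows that ordinals are summed. The size of any effect also rests on assumed puff counts.

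What does not stand is that the text is adequate as printed. The indicator reading appears in neither document. Table 8 lists what the device measures and records for each puff, where an ordinal is a natural field and a constant 1 is not. When the same table means a count, as for peaks within a puff, it says so. A derivation rule that works only on an unstated meaning of its input needs correcting.

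**Conclusion.** The point holds conditionally. As printed, and with Ni read as the ordinal, NPC is n(n+1)/2, which contradicts its own label and the limits used in the same table. If programmed that way, NPC and puff frequency would be inflated 4.5 to 8.5 times for an assumed 8 to 16 puffs, and the averages deflated by the same factors. Arm ratios would be distorted wherever puff counts differ (13/17 = 0.76 for an assumed 12 against 16).

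Severity is low. Puffing topography is exploratory in both documents. No primary or secondary endpoint, sample size or error rate depends on it. The conclusion is about the written rule, not about what the software does.

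**What to change.** In SAP Table 9, replace the formula for NPC with a definition: the count of valid puffs recorded for that product use. Do not use the highest Ni. The protocol has invalid data discarded and the SAP keeps only data the software can process. Neither says whether single puffs can be dropped, and if they are, the numbering has gaps and the highest Ni exceeds the valid count.

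Then check the derivation program against this definition for all 12 rows that use NPC. In the same check, correct the average inter-puff interval: its printed formula is ΣQci/NPC, identical to the peak flow row although the unit is seconds, and it should sum the inter-puff interval.

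The cost is a small SAP clarification and a program check. Protocol amendments go to the ethics committee (Protocol Section 1.1), and this does not warrant one by itself; Protocol Table 5 can be aligned at the next amendment.

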The descriptive statistics of the biomarkers of the primary endpoints will also be calculated per stratification factor. Reason for change: the protocol specified that primary endpoint analyses would be done by stratification factor, and this clarifies that descriptive statistics will also be presented by stratification factor.

An analysis of plasma nicotine and cotinine and NEQ will be done covering the exposure period. Reason for change: this analysis would serve to supplement the measure of difference of exposure between CC and CHTP arms over the entire exposure period.

New parameters were added to Human Puffing Topography Assessment (Number of peak(s) in the puff, Average puff volume per peak, Average puff duration per peak) in Tables 8 and 9. Reason for change: These additional parameters would improve the assesment of topography.

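### Average inter-puff interval is defined with the peak-flow formula in SAP Table 9 and protocol Table 5

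*SAP*

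**What the plan says.** SAP 7.3 makes its tables the derivation rule: "From the per-puff parameters, the per-cigarette parameters shown below will be derived". Table 8 defines the per-puff variables. Among them are Qci, the peak flow in mL/s, and Ii, the "Inter puff interval" in seconds. Table 9 then gives 19 per-cigarette parameters. The row "Total inter puff interval" is the sum of Ii. The next row, "Average inter puff interval" (variable AvgIi, unit s), has the formula "\Sigma Qci / NPC, i=1 \dots NPC", which is also the formula of the peak flow row (AvgQci, unit mL/s).

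Protocol 7.7.2, Tables 4 and 5, has the same definitions and the same formula in the same row.

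SAP section 9 reports a revision of these tables: "New parameters were added to Human Puffing Topography Assessment". It lists three peak-based additions and leaves the interval row as it was.

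SAP 12.5.3.2 sets out the use of the parameters: "The per-cigarette parameters derived from the HPT assessments will be summarized along with their changes from baseline". They are also plotted as geometric means. On Days 1 and 4 separately, each is compared between arms by ANCOVA on the log scale, reported as a percentage reduction with a 95% CI.

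**The concern.** A mean of values in mL/s cannot be a time in seconds, and two differently named parameters cannot share one formula. The same formula stands in both documents, so it looks like a row copied from peak flow and carried from the protocol into the SAP, not a fault of PDF conversion.

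If the SAP is programmed literally, the tables would present an arm difference in peak flow under the name of inter-puff interval. The numbers could look plausible, so the error might not be noticed. Time between puffs is one of the behaviours that puffing topography is meant to describe, and a reader would draw a conclusion about it from the wrong quantity.

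**Working it through.** **Inputs**

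| Item | Source | Definition | Unit |
|---|---|---|---|
| Qci | SAP Table 8, protocol Table 4 | peak flow of puff i | mL/s |
| Ii | same | interval for puff i | s |
| Di | same | duration of puff i | s |
| DFi | same | Ii + Di | s |
| AvgQci | SAP Table 9, protocol Table 5 | ΣQci / NPC | mL/s |
| TIi | same | ΣIi | s |
| AvgIi | same | ΣQci / NPC | stated as s |
| TDFi | same | ΣDFi | s |
| PFeq | same | NPC / (TDFi/60) | per min |

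**Step 1: units.** ΣQci / NPC is in mL/s; the row says s. Checking every row, 17 of the 19 in SAP Table 9 agree with their stated unit. The exceptions are AvgIi and "Average puff volume per peak". The latter is Σ(Vi/Pn)/NPC; Pn is a count, so the result is in mL, but the label reads mL/s. There only the label is wrong. In protocol Table 5 (17 rows), only AvgIi fails.

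**Step 2: the table's own identity.** DFi = Ii + Di, so TDFi = TIi + TDi. Dividing by NPC gives TDFi/NPC = ΣIi/NPC + AvgDi. Since TDFi/NPC = 60/PFeq, an average interval over NPC must equal 60/PFeq − AvgDi. The printed formula does not.

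With assumed values (12 puffs, Ii = 20 s, Di = 2 s, Qci = 40 mL/s):
- TIi = 12 × 20 = 240; TDi = 12 × 2 = 24; TDFi = 264 s.
- PFeq = 12 / (264/60) = 2.727 per min; 60/2.727 − 2 = 20 s, which equals ΣIi/NPC = 240/12.
- Printed formula: 480/12 = 40. Read as seconds, that implies a smoking duration of 12 × (40 + 2) = 504 s, against 264 s from the TDFi row.

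**Step 3: the analysis.** As printed, AvgIi = AvgQci for every product use, so every mean, change from baseline, ANCOVA estimate and CI is the same in both rows. The reported reduction is 100% minus the CHTP:CC ratio of peak flow, whatever the intervals are. If, for example, the true interval ratio were 0.50 (reduction 50%) and the peak-flow ratio lay between 0.80 and 1.25, the interval line would show between 100% − 80% = 20% and 100% − 125% = −25%.

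**Step 4: the planned model on simulated data.** Assumptions: 80 subjects, 12 puffs each; median peak flow 45 mL/s and median interval 20 s. On the post-randomization day, the log values in the CHTP arm were shifted by +0.2 (flow) and −0.5 (interval). The model was log parameter on log baseline, sex, consumption stratum and product.

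| Row | Geometric mean | Reduction | 95% CI |
|---|---|---|---|
| Peak flow | 51.056 | −24.62% | −28.73 to −20.63 |
| Interval, as printed | 51.056 | −24.62% | −28.73 to −20.63 |
| Interval, ΣIi/NPC | 16.881 | 37.63% | 34.20 to 40.89 |

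Here the printed formula even reverses the direction. The first two rows are identical for any data; the distance to the third depends on the assumed values.

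**The case against.** The error is plain, but harm is not certain. The label, the variable name, the unit and the row directly above all point to Ii, and a programmer would have to overlook all four. Nor do the documents say who computes AvgIi. SAP 7.3 sends the topography data through analysis software, and protocol 7.7.2 has the sponsor's topography group validate them first, so the printed formula may never be coded.

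The stakes are also small. Topography is exploratory and appears neither among the topline outputs (SAP 13.3) nor among those considered for registry reporting (SAP 13.5). Total inter-puff interval, puff count and puff frequency are analysed alongside, and per-puff and per-cigarette values are listed. The average could therefore be rebuilt as TIi/NPC, and a duplicated row could be spotted.

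All of this stands as a limit on likelihood and importance. It does not make the specification right. The SAP says that the parameters are derived as shown, and a rule that must be disregarded to obtain the right answer should be corrected.

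One further point stands. The documents do not say whether an interval is recorded for the first or last puff. If one puff has none, the mean of the recorded intervals needs NPC − 1, not NPC. With 11 intervals of 20 s in 12 puffs, 220/12 = 18.3 s and 220/11 = 20 s.

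**Conclusion.** The point holds. The AvgIi formula in SAP Table 9 and protocol Table 5 is wrong as written: it contradicts its own name and unit and the row above it, and it duplicates peak flow. Programmed literally, 2 of 19 rows would be identical and the average inter-puff interval would not be analysed. This needs no assumed value. The size of the resulting misstatement does depend on assumed values and cannot be derived from the documents; the illustrations show only that the reported figure need not resemble the true one in size or sign.

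The effect is confined to one exploratory parameter. The rows for total interval, total smoking duration, puffing intensity, puffing time index and puff frequency do not use AvgIi and are unaffected. It should be corrected, but it is not critical to the trial's conclusions.

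**What to change.** In SAP Table 9, set AvgIi = ΣIi / NPC, which follows the table's convention for averages. State how the first or last interval is handled, so that the choice between NPC and NPC − 1 is explicit. Add a line to SAP section 9 noting that the formula in protocol Table 5 is corrected by this change. That avoids a protocol amendment, which under protocol 1.1 would have to go to the ethics committee; Table 5 itself can be corrected if the protocol is amended for another reason. If topography software supplies AvgIi, confirm that it uses Ii.

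The following can be tidied in the same pass; none changes a correctly computed value:
- Change the unit of "Average puff volume per peak" from mL/s to mL.
- Describe NPC as the number of valid puffs. The printed ΣNi is wrong only if Ni is read as the puff's ordinal number; 12 puffs would then give 1 + 2 + … + 12 = 78.
- Check the gram label on the NEQ formula in SAP 7.1.2 against the source file. Its divisor of 1000 µg/mg yields mg, but the label may have lost a character in PDF conversion.

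The cost is one symbol in SAP Table 9, a sentence on the denominator, one line in section 9 and up to three label or wording checks. No new data are needed and the analysis model is unchanged.
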